### ***D3 Point of Care CGM Placement and education***

Participants will be provided with a Dexcom G6 CGM, which will be placed during the clinic visit by diabetes staff, and CGM education will be provided at the point of care by the nurse/Certified Diabetes Care and Education Specialist (CDCES). Additionally, participants will download apps on their smartphones including Dexcom G6 and Dexcom Clarity. Caregivers and family members will download Dexcom Follow (optional). Education will be provided on using all the apps. Participants' Dexcom Clarity app will be connected to the clinic's Clarity account for remote viewing of data. Participants without a compatible smartphone will be provided a loaner smartphone for the duration of the 10-day CGM use.

### ***D4 Safety and Adverse Events***

#### **4.a Safety and Compliance Monitoring**

Site investigators will monitor compliance with the protocol and good clinical practice (GCP) guidelines.

#### **4.b Medical Monitoring for adverse events**

Participants will be monitored for adverse events during the study visit, during their CGM wear, and during the follow-up period of up to 6 months.

#### **4.c Definitions of Adverse Events**

An adverse event (AE) is defined as any untoward medical occurrence in a patient or clinical investigation subject.

#### **4.d Classification of Events**

- Relationship**

Medical judgement should be used to determine the relationship, considering all relevant factors, including pattern of reaction, temporal relationship, de-challenge or re-challenge, confounding factors such as concomitant medication, concomitant diseases and relevant history.

- **Severity**

The severity of the AE should be judged based on the following:

Mild: Awareness of sign(s) or symptom(s) that is/are easily tolerated

Moderate: Sufficient discomfort to cause interference with usual activity

Severe: Incapacitating or causing inability to work or to perform usual activities

#### **4.e Data Collection Procedures for Adverse Events**

All enrolled participants will be monitored for untoward incidents (e.g., “Adverse Events”) occurring during the study. The Principal Investigator (and other designated individuals, if necessary) will conduct regular monitoring for safety concerns and provide general oversight for human subject safety requirements during the study visit and followup period. All adverse events that are anticipated or described in the informed consent form will be logged appropriately and reported to the IRB on at least an annual basis (e.g., at continuing review).

#### **4.f Reporting Procedures**

Any Unanticipated Problems or unexpected “Serious Adverse Events” related to the study intervention or in the follow-up period, will be reported to the IRB promptly. Unplanned and non-emergent deviations from the IRB approved protocol will be logged and reported to the IRB annually at continuing review; all planned deviations will be submitted as a Change in Research to the IRB for approval and prior to implementation. All other event reporting requirements will be followed and all necessary parties will be notified of events/problems encountered in the study and/or changes in research, in accordance with all applicable regulations and guidelines.

#### **4.g Adverse Event Reporting Period**

Any Unanticipated Problems or unexpected “Serious Adverse Events” related to the study intervention and/or test article and affecting the risk/benefit profile of the study, will be reported to the IRB promptly, and, in all cases, within 10 business days of discovery.

#### **4.h Post-study Adverse Event**

Not applicable

### **E. Statistical Plan**

#### ***E1. Sample Size Determination and Power***

We calculated the sample size to detect a 10% difference in TIR from the first 5-days compared to the second 5 days of CGM wear. Assuming a TIR SD of 18% (20), a 2-sided alpha level of 0.05 and 80% power, a sample size of 28 participants was required. Allowing for 30% attrition, we planned to recruit 40 participants.

---

## ***E2. Interim Monitoring and Early Stopping***

Interim monitoring will be performed by the study team. No early stopping rules planned for this study.

## ***E3. Analysis Plan***

Primary outcome variable.

The primary outcomes of the study were change in TIR from the first 5 days compared to the second 5 days of CGM wear, and change in HbA1c level from baseline to follow up at 3-6 months, both assessed with paired *t*-tests.

Secondary outcome variables.

Secondary endpoints included behavioral modification assessed via questions during 5-day and 10-day follow up call. Change in patient-reported outcomes through surveys assessing quality of life and diabetes-distress compared between baseline and follow-up after trial CGM use.

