**2.e Risks and Benefits**

This study involves no more than minimal medical risk to the participants as use of CGM is considered standard of care per the American Diabetes Association guidelines.

Risks associated with use of CGM may include hypoglycemia (low blood sugar) or hyperglycemia (high blood sugar) in cases where information provided by the CGM device is inaccurate and used to make treatment decisions or where hardware or set-up issues disable alarms and alerts. Patients will be advised to confirm with a fingerstick blood sugar if symptoms do not match CGM readings.

Patients may also experience skin irritation or redness around the CGM device's adhesive patch. The CGM may inadvertently fall off, and if that occurs, the patient will resume checking fingerstick blood sugars as they were previously.

To minimize risk, when the diabetes nurse/CDCES places the CGM, the nurse will perform routine standardized education including setting up alerts. The CGM devices provide blood sugars every 5 minutes (that creates a continuous reading) versus the typical 4-5 fingerstick blood sugars usually checked per day. Therefore, the CGM actually minimizes risk of hypoglycemia by alerting users to impending hypoglycemia which may not have been previously detected. Participants will have been taught signs/symptoms of hypoglycemia per routine new-onset diabetes education. They will be educated to check blood sugar via fingerstick if they have any sign/symptoms of hypoglycemia and treat accordingly. If they do not understand how to use the device, they have access to Pediatric Endocrinology on-call provider and Dexcom customer service for assistance, and device may be removed early. The risk of device malfunction is extremely low.

The CGM will be applied in clinic by diabetes nursing staff. If patient reports any irritation or signs of infection at the site, the CGM will be removed early. If the CGM is removed early either accidentally or intentionally, participants will be offered a replacement CGM. They will have to resume previous blood sugar monitoring with glucometer and fingersticks, as the patient was using prior to placement of CGM.

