**Confidentiality:** There is the risk that psychological, emotional, financial, social, and legal risks might result if confidentiality cannot be maintained in this study. All study team members are HIPPA trained and will take every step to respect participants' privacy and protect their confidentiality throughout the study. We share the information gathered in the study only with the people who need to know this information. All information gathered during this study will be kept in a secure HIPAA compliant database, REDCap.

**Benefit:** Use of CGM may increase blood sugar monitoring, reduce hypoglycemia, and improve glycemic control.

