### **D2 Schedule of Procedures**

**Eligibility and Consent:** If the patient is eligible and interested in the study, the research coordinator will meet with the patient and caregiver in an exam room for privacy and confidentiality. The research coordinator will explain the study and study procedures, read the informed consent form with the participant and caregiver, and allow time for questions on the study and consent form.

If the participant is less than 18 years of age, the parent will sign the consent form and the participant will sign the assent. If the participant is 18 years of age or over, the participant will sign the consent.

At the time of consent, 3 phone numbers are collected from the participant for future follow-up.

At the baseline visit, barriers to prior CGM use or sustained use will be recorded.

The certified diabetes educator (CDCES) will place the CGM and provide standardized education, including education on use of the Dexcom apps, including Dexcom G6 Dexcom Clarity, and Dexcom Follow (optional) for caregivers. The participant's Dexcom Clarity account will be connected to the clinic portal for remote viewing of data.

The nurse/CDCES will follow up with the patient by phone in 5 days (4-6 days if day 5 falls over a weekend) and again at 10 (9-11) days at the end of the CGM session. Assessment and education during these follow-up phone calls will include report of behavior changes related to blood glucose monitoring and insulin administration, and nurse/CDCES recommended dose adjustments based on observed patterns, as well as education on obtaining personal CGM. CGM data (when available) will be recorded.

---

At the participant's next follow-up visit at 3 months (or up until 6 months if a visit is cancelled), use of personal CGM will be recorded, in addition to Hemoglobin A1c measured at that visit, questions about behavioral changes, and CGM data, if available.

Questionnaires will be administered before and after initiation of the CGM and at their routine diabetes clinic visit 3-months later to assess changes in psychosocial outcomes of diabetes distress and hypoglycemia worry. Surveys will be administered via REDcap survey.

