## ***E4. Statistical Methods***

Categorical variables will be described using frequencies and percentages. The Shapiro-Wilks test will be used to assess the normality distribution of continuous variables.

Normally distributed variables will be described by mean and standard deviation. Non-normally distributed variables will be described by median and interquartile range. Paired *t*-tests will be used to assess most differences between baseline and follow up. Wilcoxon signed rank tests will be used for the Diabetes Distress Scale scores and sub-scores.

Time in range data from the first 5 ( $\pm 1$ ) days of CGM wear will be compared to the second 5 ( $\pm 1$ ) days for any patients with at least 8+ days of CGM wear. Additional comparisons will be made with the follow-up CGM data recorded at the 3 or 6-month follow-up. Three month follow up data will be used when available. If the 3-month visit is missing, but there is a later 6-month follow-up, the 6-month visit data will be used. Two sample *t*-tests, and Wilcoxon rank sum tests (for the Diabetes Distress Scale), will be used to assess differences between groups in survey responses. The values  $p < 0.05$  are considered statistically significant. Statistical analysis generated using SAS version 9.4

Copyright © 2020 SAS Institute Inc., Cary, NC.

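### No planned analysis covers time below range or hypoglycemia events, so a gain in time in range cannot be read for low glucose

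*Combined protocol and SAP*

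**What the plan says.** E3 gives two primary outcomes. The first is TIR: "The primary outcomes of the study were change in TIR from the first 5 days compared to the second 5 days of CGM wear". The second is HbA1c: "change in HbA1c level from baseline to follow up at 3-6 months, both assessed with paired" *t*-tests. The secondary outcomes are behavior ("Secondary endpoints included behavioral modification assessed via questions during 5-day and 10-day follow up call") and surveys ("Change in patient-reported outcomes through surveys assessing quality of life and diabetes-distress compared between baseline and follow-up after trial CGM use").

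E4 repeats the TIR comparison "for any patients with at least 8+ days of CGM wear" and adds comparisons with follow-up CGM data, without naming a metric for them. Section E mentions neither time below range nor time above range. It has no count of hypoglycemic episodes and no analysis of adverse events. No glucose limits are given for TIR itself.

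Other sections show why low glucose is relevant:

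- 2.b excludes patients who are not on insulin.
- D2 says the day-5 and day-10 calls include "nurse/CDCES recommended dose adjustments based on observed patterns".
- 2.e says "Risks associated with use of CGM may include hypoglycemia (low blood sugar) or hyperglycemia (high blood sugar" and ties this to acting on inaccurate sensor values or to disabled alerts. Its benefit paragraph says "Use of CGM may increase blood sugar monitoring, reduce hypoglycemia, and improve glycemic control".

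D4 provides for monitoring adverse events during wear and for up to 6 months, grading their severity and logging them for the IRB. D2 also lists a questionnaire on hypoglycemia worry, which E3 does not name.

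**The concern.** B1 defines better glycemic control as change in TIR and HbA1c. Neither measure separates low glucose from high. TIR can rise while time below range also rises, provided time above range falls by more. HbA1c tracks average glucose, so a fall does not show whether lows became more or less frequent.

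This matters in an insulin-treated group because dose advice may be given at day 5 (day 4 to 6 around a weekend), which is where the primary contrast divides the wear period. Followed as written, the plan could report better control in the second half and be unable to say which way low glucose moved, although the sensor records would show it.

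The existing items only partly cover this. Adverse-event logging may catch reported episodes, but it has no planned analysis and would miss lows without symptoms. Hypoglycemia worry is a psychosocial score, not a glucose measurement.

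**Working it through.** **1. The plan's own figure.** E1 gives a difference of 10 points, SD 18, two-sided alpha 0.05, power 80% and n = 28. Take 18 as the SD of the within-person difference.

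- Normal approximation: (18 × (1.960 + 0.842) / 10)² = 25.4, so 26.
- Exact paired *t*: power is 79.4% at n = 27 and 80.9% at n = 28, so 28.
- Attrition: 28 / (1 − 0.30) = 40.

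Both stated figures reproduce. The point does not depend on them, and the fix does not change them.

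**2. What the TIR test can see.** For each person and period, TIR + time below range (TBR) + time above range (TAR) = 100%. Hence

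change in TIR = −(change in TBR) − (change in TAR).

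Set the change in TIR to E1's 10 points (10% of 24 h = 2.4 h/day). The TBR values are illustrative. One percent of a day is 14.4 minutes.

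| Change in TBR | Change in TAR | Change in TIR | Change in low glucose |
|---|---|---|---|
| −2 | −8 | +10 | −28.8 min/day |
| +1 | −11 | +10 | +14.4 min/day |
| +2 | −12 | +10 | +28.8 min/day |
| +4 | −14 | +10 | +57.6 min/day |

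The paired test on TIR uses only the third column, so it gives the same result in every row.

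**3. Are the data there?** 2.e says the sensor reads every 5 minutes: 288 readings a day, up to 5 × 288 = 1,440 per person in each 5-day period. D2 says CGM data are recorded when available, and the participant's account is linked to the clinic portal. Readings within a person are serially correlated, so their number shows that TBR can be calculated, not how precise it is across participants.

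**4. Precision with 28 participants.** The documents give no SD for the change in TBR, so a range is assumed. Half-width of the 95% CI for a mean = t(27; 0.975) × SD / √28, with t = 2.052 and √28 = 5.292.

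| Assumed SD of change (points) | Half-width (points) | Half-width (min/day) |
|---|---|---|
| 1 | 0.39 | 6 |
| 2 | 0.78 | 11 |
| 3 | 1.16 | 17 |
| 4 | 1.55 | 22 |
| 5 | 1.94 | 28 |

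These are approximate. TBR is likely to be skewed with many values near zero, so an interval for the median will differ somewhat.

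**The case against.** The strongest reply is that the addition cannot test what 2.e asserts. Both 5-day periods are on CGM, and eligible participants have used none for 12 months, so there is no pre-CGM sensor record to compare with. The risk in 2.e also arises partly from sensor inaccuracy, which the same sensor cannot reliably reveal. Both points stand. A reader might infer that the recorded data could confirm or refute the claimed reduction in hypoglycemia; they cannot. They can describe change during wear.

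Second, safety is not ignored. D4 monitors, grades and logs adverse events, and symptomatic hypoglycemia could be captured there. That stands too. What is missing is a planned analysis and any view of lows without symptoms.

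Other stronger readings are also unsupported:

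- *Hypoglycemia is the main risk.* 2.e names it together with hyperglycemia, conditionally, and describes the study as no more than minimal risk.
- *Participants with under 8 days of wear drop out of all CGM analysis.* E4 attaches that rule to the first-versus-second-half comparison. The follow-up comparison does not repeat it, and 2.e offers a replacement sensor.
- *Both calls can affect the TIR contrast.* The day-10 call comes at the end of the session, so only the day-5 call can affect days 6 to 10.
- *No claim of improved control should be made without TBR.* B1 defines control by TIR and HbA1c, and such a bar would set no criterion.

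**Conclusion.** The point holds as a gap in what is analysed and reported. The primary tests are not invalid. TIR is the only CGM metric named, and nothing in section E would show whether time below range rose or fell. A 10-point TIR gain is compatible with either: for example, 28.8 minutes a day more low glucose or 28.8 minutes a day less.

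The identity in step 2 needs no assumption. The TBR changes entered in it are illustrations, and the precision of 0.8 to 1.6 points rests on an assumed SD of 2 to 4 points. A reader might infer that a TIR gain in this trial did conceal more hypoglycemia. The documents show only that the planned outcomes could not rule it out. The change is worth making because it costs little and lets the conclusion on glycemic control be read for safety.

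**What to change.** In E3 and E4:

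- State the glucose cut-points that define TIR.
- Add, as a descriptive safety outcome, percent time below range and percent time above range for the first and second 5 days, and for follow-up CGM where available.
- Give the paired median change with a 95% CI, by a signed-rank method or bootstrap.
- Add a descriptive summary for everyone with any sensor data, whatever the length of wear.
- Add a count of hypoglycemia adverse events from the D4 log.
- Present these beside the TIR and HbA1c results.
- State that, with no pre-CGM sensor data, this describes change during wear and cannot test whether CGM reduces hypoglycemia.

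The cost is a few lines of text and one extra table, with no added participants, visits or devices. The downside is limited precision on a skewed measure, so the result should be read as an estimate and not as a powered test.

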### A2 Primary Hypothesis

We hypothesize that providing sample complementary CGM at the point of care with standardized CGM education will improve glycemic control in pediatric patients with type 2 diabetes.

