## B Study Objectives

### B1 Primary Aim

To determine if 10-day trial CGM use in youth with T2D improves glycemic control (changes in time in range and Hemoglobin A1c).

---

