## **C Study Design**

### ***C1 Overview of Study Design***

This is a hypothesis-driven, pre-registered, prospective cohort study to determine if point of care placement of complementary CGM with standardized CGM education improves glycemic control.

The study will consist of a baseline visit (coincident with routine clinical care) where a complementary trial CGM is placed at the point of care with standardized CGM education. CGM-related apps will be downloaded on the participant's smartphone. Follow-up phone calls will be conducted by the study team at 5-days and 10-days after CGM placement. CGM data will be recorded at the next follow-up visit (if available) and hemoglobin A1c level (performed as part of routine clinical care) recorded. Surveys will be completed at baseline, 10-days (via email), and at follow-up (3-6months)

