### ***C2 Subject Selection and Withdrawal***

#### **2.a Inclusion Criteria**

- Patients with type 2 diabetes for more than 3 months
- Ages 8-21 years
- CGM naive or no CGM use in the 12 months prior to enrollment
- No minimum A1C level required for eligibility.

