#### **2.b Exclusion Criteria**

- CGM use in the 12 months prior to enrollment
- Participants with T2D not on insulin

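### The powered TIR outcome compares two periods that are both on CGM, so by itself it cannot show whether CGM improved glycemic control, as B1 takes it to

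*Combined protocol and SAP*

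**What the plan says.** Section A2 hypothesizes that CGM supplied at the point of care with education "will improve glycemic control in pediatric patients with type 2 diabetes". Section B1 sets the primary aim as finding out whether the 10-day trial "improves glycemic control (changes in time in range and Hemoglobin A1c"), so change in TIR is one of its two named measures of improvement.

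Section E3 makes the TIR outcome the "change in TIR from the first 5 days compared to the second 5 days of CGM wear". E1 sizes the study on that contrast and E4 repeats it, allowing 1 day either way in each window and requiring at least 8 days of wear. E3 also makes HbA1c change, from baseline to 3-6 months, a primary outcome. E4 adds a comparison with CGM data recorded at follow-up.

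On timing, C1 describes a baseline visit at which "a complementary trial CGM is placed at the point of care with standardized CGM education", and D2 and D3 agree. At placement, section 2.e says, "the nurse will perform routine standardized education including setting up alerts". D2 schedules a nurse or educator call at about day 5, which includes education and dose recommendations.

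On the reference state, eligibility in 2.a requires "CGM naive or no CGM use in the 12 months prior to enrollment", and 2.b repeats this as an exclusion. C1 says: "This is a hypothesis-driven, pre-registered, prospective cohort study". Section 2.d marks randomization and blinding as not applicable. No run-in, pre-CGM TIR or comparison group is described.

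**The concern.** The word *improves* in B1 is naturally read as better than before the trial CGM. No TIR value in the plan comes from before it. CGM, education, apps and alerts are all in place when the first window opens, so that window is not a baseline. The follow-up comparison in E4 is also made with CGM data and lacks a pre-CGM value in the same way.

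The contrast therefore captures further change during wear under the whole package of CGM, education and calls. The day-5 call falls about where the two windows meet. B1, E3 and E4 do not say this.

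What is at stake is the reading of the only outcome on which the sample size is built. A null TIR result could be reported as no benefit from CGM, although a benefit present from the start would cancel out. A significant result could be reported as improvement over earlier monitoring, although the earlier level was never observed.

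**Working it through.** **Inputs, all from E1.** Difference to detect: 10 percentage points of TIR. SD: 18 points, without saying whether this is the SD of one window or of the paired difference. Two-sided alpha 0.05, power 80%. Required n = 28, with 40 to be recruited after 30% attrition.

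**Step 1: reproduce the plan's figure.**
- Two-sided paired t-test (noncentral t), with 18 as the SD of the difference: power is 79.4% at n = 27 and 80.9% at n = 28. So 28 is the smallest n that reaches 80%.
- Attrition: 28 / (1 − 0.30) = 40.
- A comparison of two independent means would need 51 per group, so E1 is a paired, within-wear calculation. Its arithmetic is sound.

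**Step 2: what the contrast estimates.** Let *m* be a participant's pre-CGM TIR and *b(d)* the change from *m* on day *d* of wear. Then

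contrast = [*m* + mean of *b* over days 6-10] − [*m* + mean of *b* over days 1-5] = mean *b*(6-10) − mean *b*(1-5).

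The pre-CGM level *m* drops out. No result of this test can recover it.

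**Step 3: illustration.** The documents give no onset day, so the onset is assumed. The benefit is a sustained 10 points, n = 28, SD of the difference 18.

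| Benefit starts | Mean, days 1-5 | Mean, days 6-10 | Contrast | Significant |
|---|---|---|---|---|
| Day 1 | 10 | 10 | 0 | 5% |
| Day 3 | (0+0+10+10+10)/5 = 6 | 10 | 4 | 20.5% |
| Day 6 | 0 | 10 | 10 | 80.9% |

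The eventual benefit over the pre-CGM state is 10 points in every row. The full 10 points used in E1 appear only if nothing happens until the second window opens. The contrast needed for 80% power is 9.89 points. With a day-3 start, 0.4 of the benefit reaches the contrast, so the benefit would have to be 9.89 / 0.4 = 24.7 points.

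**Step 4: the other direction.** A rise from *m* to *m* + 10 gives a contrast of 10. A recovery from *m* − 10 to *m* also gives 10, with no gain over the pre-CGM state. The test cannot tell these apart. This is a point of logic; the documents do not suggest that TIR falls at placement.

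**Step 5: sensitivity.**
- *SD.* If 18 is the SD of one window, the SD of the difference is 18 × √(2(1 − ρ)), where ρ is the correlation between windows. It is 18.0 at ρ = 0.5 (results unchanged) and 13.9 at ρ = 0.7, where the 4-point contrast is significant about 31% of the time. The day-1 contrast is 0 in each case.
- *Window split.* With 10 days of wear and the split after day 4, 5 or 6, the day-1 contrast stays at 0. The day-3 contrast is 5.0, 4.0 or 3.3 points (29.4%, 20.5% or 15.7%).

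**The case against.** There is a serious case on the other side.

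- *The contrast is open and consistent.* E1, E3 and E4 all define it the same way, so no analyst would run the wrong test. A limit on interpretation often goes in the report's discussion. This stands in part: no n, test or p-value changes, which keeps the matter below the most serious grade. But B1 assigns the contrast a meaning it does not have, and that belongs in the plan.
- *HbA1c covers the pre-CGM question.* It is a primary outcome and starts from baseline. This stands. A reader might infer that the whole trial lacks a pre-CGM reference, and the documents do not support that. The limit is on TIR.
- *Neither A2 nor B1 names a comparator.* A1 describes a pilot in which glucose feedback leads to changed behavior, and early against later wear is a defensible measure of that process. This is a good reason to keep the contrast. It is not a reason to call the result improved glycemic control without qualification.
- *The numbers rest on assumed onset days.* They do, and only the day-1 zero is free of the SD and of the window split. A reader might add late-onset cases, such as a benefit starting on day 8 or 10, as further evidence. They are not: those contrasts are small because the wear is short, and would be small even with a pre-CGM value.

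**Conclusion.** The point holds for the TIR outcome and should be fixed. As written, the only outcome with a sample size calculation does not measure what B1 says it measures. By itself it can show neither improvement nor lack of improvement over pre-CGM monitoring.

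That conclusion follows from the timing of the windows and needs no numerical assumption. Its possible size does need one. For a 10-point sustained benefit, the measured contrast is 0 with onset on day 1 and 4 points with onset on day 3, given n = 28 and an SD of the difference of 18.

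Two stronger readings go too far. A reader might infer that the sample size is wrong, but 28 and 40 both reproduce for the contrast as defined. A reader might also infer that A2 cannot be addressed at all, but HbA1c partly addresses it, as an uncontrolled pre-post change. Whether HbA1c is adequately powered, and how dose advice or later personal CGM use might affect it, are separate questions.

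**What to change.** Keep the windows, the paired t-tests, the sample size and both primary outcomes.

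1. In B1, E3 and E4, label the TIR outcome *within-wear change in time in range*.
2. In E3, add: *The TIR outcome is the change from the first to the second 5 days of wear under CGM, education and follow-up calls and has no pre-CGM value; a null result does not show that CGM has no benefit, and a significant result does not show improvement over pre-CGM monitoring. Change from the pre-CGM state is assessed only by HbA1c, as an uncontrolled pre-post change.*
3. In E4, note that the 3-6 month CGM comparison also has no pre-CGM value.
4. A1 and E3 are partly in the past tense. If data already exist, date the new wording and mark it as a limit on interpretation.

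The cost is wording, with no new data or tests. Because B1 is the stated primary aim of a study described as pre-registered, the change there should be recorded as an amendment. The downside is that the claim from the powered outcome becomes narrower.
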